Sample Size: The primary outcomes are the clinic attendance rate and the change in diabetes-related distress, as measured by the Diabetes Distress Scale (DDS) and PAID-5 scale between the ED visit and the follow-up appointment date (19). Secondary outcomes include repeat ED/EMS utilization over 6 months, repeat hospitalizations, major cardiovascular events, and changes in hemoglobin A1c. For clinic attendance, we will aim to achieve attendance at 80% of the scheduled clinic visits. For a one-sided test at alpha=0.025 of a single proportion against a standard proportion (0.80), we will have 80% power to detect a difference of 0.13 (0.80 – 0.67) with a sample size of 83 subjects in the CGM group. Adjusted for 20% dropout, we will need approximately 100 subjects/group. For the DDS outcome, we will compare the change from baseline to the end of follow-up in the DDS between the two groups. Although we will fit the trajectory of the DDS change in each group using all DDS measures in a mixed effects model with repeated measures (MMRM), for simplicity in sample size estimation, we will calculate the sample size for an unadjusted comparison of the change between the two treatment groups. Based on a study of 267 subjects with diabetes (19), the standard deviation of the DDS was 1.0 across the three sites in that study. The DDS is a questionnaire of 17 questions, each scored on a Likert scale of 1 (not a serious problem) to 6 (serious problem), with the overall score calculated as the mean score across the 17 items. Thus, the range of the overall score is 1.0 – 6.0. With 100 subjects in each group, we can detect a difference of about 0.40 in the DDS change between the two groups. The literature on the DDS does not identify a clinically meaningful difference although Fisher, Polonsky, Hessler, Mullan (2012) suggest a difference of 0.5 as meaningful (20). Thus, our sample size will achieve power of greater than 80% to detect that difference.

Analysis Strategy: As indicated in the Sample Size section above, for the clinic attendance rate, we will conduct the initial unadjusted analyses using an exact test of the frequencies under the presumed population proportion (0.80) and the observed proportion. Adjusted analyses will be conducted using a logistic regression model for the proportion of clinic visits attended as the outcome in the intervention group with predictors including age, gender, time since diagnosis of diabetes, and other factors of interest.

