For the outcome of change in DDS, we will conduct the initial unadjusted analysis as described above in the Sample Size section. For adjusted analyses, we will include each DDS score in the longitudinal MMRM, so that we can model the trajectory of change as well as the individual changes over the period of follow-up. The time metric in this model will be the time (months) since study enrollment with predictors including age, gender, time since diagnosis of diabetes and other factors of interest. We will also investigate subgroups of interest using a Forest plot approach. We will plot the means and confidence intervals for the outcome for the two groups using Forest plots to display the total groups and subgroups of interest. We will also generate

longitudinal plots of A1c over time with the means and appropriate exact 95% confidence intervals at each time point. In addition, with the DDS trajectories available, we are able to use machine-learning approaches, such as growth mixture models, to identify clusters of patients with similar trajectories but who are not members of previously defined subgroups. Finally, we will conduct sensitivity analyses to determine if missingness of DDS scores are missing at random or missing not at random. For these analyses, we will use several methods, including the jump-to-reference imputation and the pattern mixture model approaches, to determine if the results using the sensitivity analyses are consistent with the MMRM results, indicating that the missingness is missing at random.

For the secondary outcomes, the change in HbgA1c will be modeled as for the DDS above. The other secondary outcomes can be modeled as binary outcomes and will be modeled as longitudinal logistic models.

Data Management Plan:

All study data will be recorded on a REDCap database established on a secure encrypted server on AWS. All access to the database will be through permissions established by the IT REDCap administrator. Investigators will have to log into the REDCap database to enter or view data. The REDCap database will be developed and implemented by the data management staff of the UMMS Quantitative Methods Core (QMC) with the direction of [name], QMC Director. Logic data checks will be built into the data entry process to help clean the data at entry. Quality control edits will be run to identify inconsistencies and questionable values in the data. The audit trail will be activated for the duration of the study.

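### Neither planned analysis of change in DDS, a primary outcome, is specified to condition on the baseline score, so precision available at no cost is not secured

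*Combined protocol and SAP*

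**What the plan says.** Section 10 (Study Endpoints) and Section 13 (Sample Size) make change in DDS a primary outcome. Sections 9 and 11 schedule the questionnaire twice, at enrolment and at the follow-up visit around Day 14-21. The six-month step is record abstraction without patient contact.

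Section 13 describes two DDS analyses.

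- **Unadjusted change.** Sample Size says the MMRM will be fitted, but that "for simplicity in sample size estimation, we will calculate the sample size for an unadjusted comparison of the change between the two treatment groups". It concludes: "With 100 subjects in each group, we can detect a difference of about 0.40 in the DDS change between the two groups". Analysis Strategy then makes this comparison the starting point: "For the outcome of change in DDS, we will conduct the initial unadjusted analysis as described above in the Sample Size section".
- **Adjusted MMRM.** Here "we will include each DDS score in the longitudinal MMRM, so that we can model the trajectory of change", so the baseline score enters as one of the responses. The covariates are "predictors including age, gender, time since diagnosis of diabetes and other factors of interest". The missing-data sensitivity analyses are run "to determine if the results using the sensitivity analyses are consistent with the MMRM results".

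Neither analysis is called primary. Baseline DDS is not listed as a covariate. No arm term, arm-by-time term or structure for the baseline means is written out for the MMRM.

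**The concern.** In a randomised trial with one baseline and one follow-up measurement, conditioning on the baseline score is in large samples never less precise than subtracting it, and usually more so. The score is already collected, so the gain needs no extra patients or visits. Listing demographic covariates does not secure it. Whether the MMRM secures it depends on how the baseline means are modelled, and the plan leaves that open. At stake is power on a primary outcome, particularly if a fifth of follow-up scores are lost.

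**Working it through.** **Inputs from Section 13:** 100 per group; SD of the DDS 1.0; difference of 0.40 stated as detectable; 0.5 taken as meaningful; 20% dropout, stated for the attendance outcome.

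**Assumptions:** two-sided alpha 0.05 (none is stated for DDS); 1.0 read as the SD of a single score, equal at both visits; the 20% loss applied to follow-up DDS completely at random, giving 100 baseline and 80 follow-up scores per group; r = 0.3, 0.5 or 0.7.

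**Step 1: the plan's own figure.** (1.960 + 0.842) × 1.0 × √(2/100) = 0.396, or 0.398 with the t distribution. Power for 0.5 is 94%. Both statements in the plan reproduce. The calculation uses 1.0 as the SD of the change. Since SD(change) = SD(score) × √(2(1−r)), a score SD of 1.0 gives a change SD of 1.0 only at r = 0.5.

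**Step 2: variance per arm, score SD 1.**

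- Change score: 2(1−r)/80
- MMRM, visit as a category, free baseline means: (1−r²)/80 + (1−r)²/100
- ANCOVA, or MMRM with a common baseline mean: (1−r²)/80

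ANCOVA relative to change score: (1−r²)/[2(1−r)] = (1+r)/2 = 0.65, 0.75, 0.85.

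**Step 3: results.** The SE of the arm difference is √(2 × variance per arm). Power is from the noncentral t.

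| | r = 0.3 | r = 0.5 | r = 0.7 |
|---|---|---|---|
| SE: change / free MMRM / adjusted | 0.187 / 0.180 / 0.151 | 0.158 / 0.154 / 0.137 | 0.122 / 0.121 / 0.113 |
| Power for 0.40 | 57% / 60% / 75% | 71% / 73% / 83% | 90% / 91% / 94% |
| Difference detectable at 80% power | 0.527 / 0.509 / 0.425 | 0.446 / 0.434 / 0.386 | 0.345 / 0.340 / 0.318 |
| Power for 0.5: change / adjusted | 76% / 91% | 88% / 95% | 98% / 99% |
| Change-score n per group matching 80 adjusted, 80 × 2/(1+r) | 123 | 107 | 94 |

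A simulation of 20,000 runs agreed on power for 0.40 (56.7/59.5/74.5%, 70.8/72.7/82.3%, 89.8/90.6/93.5%). Under the null each test rejected in 4.7% to 5.0% of runs.

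**Step 4: what the MMRM recovers.** In a separate simulation (2,000 runs, 100 per group, visit as a category, unstructured covariance, complete data), the model with free baseline means returned exactly the change-score estimate, with an SE of 0.137 for both at r = 0.5. The model with a common baseline mean returned exactly the ANCOVA estimate (SE 0.120). With 20% of follow-up scores missing at random, the SEs at r = 0.5 were 0.155 (change), 0.150 (free) and 0.133 (common mean or ANCOVA).

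**Step 5: other reading of the SD.** If 1.0 is the SD of the change, change-score power for 0.40 with 80 per group is 71% whatever r is. Adjusted power is 88%, 83% and 78% at r = 0.3, 0.5 and 0.7. The variance ratio is unchanged.

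**The case against.** The strongest reply has four parts.

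1. **Both analyses already use the baseline score.** One subtracts it and the other models it as a response. This stands. A follow-up-only comparison with 80 per group has 71% power for 0.40, and at r = 0.7 the change score reaches 90%. Subtraction helps whenever r exceeds 0.5. A reader might infer that the plan ignores baseline DDS, and that would be wrong. What is missing is conditioning on it.

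2. **The MMRM may deliver the gain.** This also stands. The plan neither states nor excludes a common baseline mean, and its open covariate list neither names nor excludes baseline DDS. The equality with the change score needs visit as a category, complete data and free baseline means, whereas the plan uses time in months and expects dropout. A reader might infer that the planned MMRM gains nothing, but the documents do not fix the model far enough to show that. They show only that the gain is not secured.

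3. **The text leans toward the MMRM.** It is the model that will be fitted, the unadjusted comparison is used to simplify sizing, and the sensitivity analyses are judged against the MMRM. This narrows the ambiguity but does not designate a primary analysis.

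4. **Power for the plan's meaningful difference is adequate anyway.** For 0.5, change-score power with 80 per group is 88% at r = 0.5. It falls below 80% only if r is below about 0.37 with the full 20% loss. That loss may overstate the case, because Section 11 seeks questionnaires from no-shows online, by mail or by phone. This stands as a limit on the importance of the point.

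**Conclusion.** The point holds as a free gain in precision that the plan leaves unsecured. It is not bias: the change score is unbiased and its type I error is valid. It is not a sample-size error either. A reader might infer from the power figures that the claim of more than 80% power for 0.5 fails, but the calculations support that only if r is below about 0.37 and the whole 20% is lost.

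The size depends on r, which the documents do not give. The variance falls by 35%, 25% or 15% at r = 0.3, 0.5 or 0.7. At r = 0.5, the value the plan's 0.40 implies if 1.0 is the score SD, power for 0.40 with 80 completers rises from 71% to 83%, and the change score would need about 107 completers per group to match. If r is high the gain is small. The figures assume equal SDs at the two visits and loss completely at random.

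The open covariate list, the absence of a stated PAID-5 model and the clustering work ("such as growth mixture models, to identify clusters of patients with similar trajectories") might be read as further failures of the primary analysis. They are missing detail or exploratory, and this conclusion does not rest on them.

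**What to change.** In Analysis Strategy, name one primary DDS analysis:

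- ANCOVA of the follow-up score on arm and baseline score; or
- a two-visit MMRM with visit as a category and baseline means constrained equal across arms.

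State the treatment contrast at the follow-up visit. The plan now says "The time metric in this model will be the time (months) since study enrollment". If time stays continuous, the coefficient is a per-month slope and must be converted to a difference at that visit before it can be read against 0.40 or 0.5.

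Keep the unadjusted change comparison as supportive, and apply the same baseline adjustment to PAID-5. Keep the missing-data sensitivity analyses and the questionnaire outreach to no-shows, because baseline adjustment does not deal with missingness tied to attendance.

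The cost is SAP wording, with no new data, visits or patients.

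### The DDS subgroup forest plots are specified as arm means with confidence intervals; no subgroup-level CGM effect or arm-by-subgroup interaction estimate is planned

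*Combined protocol and SAP*

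**What the plan says.** The plan for DDS subgroups takes up a few lines of section 13, Analysis Strategy. The method is given as "We will also investigate subgroups of interest using a Forest plot approach", and the display as "We will plot the means and confidence intervals for the outcome for the two groups using Forest plots", for the total groups and for subgroups of interest.

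The adjusted longitudinal model for DDS has "predictors including age, gender, time since diagnosis of diabetes and other factors of interest". No arm-by-subgroup term is named there or elsewhere.

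The Sample Size text of the same section defines the DDS comparison as a between-arm contrast: "we will compare the change from baseline to the end of follow-up in the DDS between the two groups". That contrast is described for the whole sample only.

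Candidate subgroups (diabetes type, new diagnosis, presentation with hypo- or hyperglycemia) are listed only under Provider Data. That part is descriptive and gives no method for comparing effects between subgroups.

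**The concern.** A subgroup forest plot is normally read for two things: the treatment effect within each subgroup, and whether that effect differs between subgroups. As worded, this one displays neither. It shows how distressed each arm is in each subgroup, with an interval that describes the arm and not the contrast between arms.

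Two misreadings follow easily. A reader may compare the two arm intervals by eye, which is a conservative way to judge a difference. Or a reader may see the arms well apart in one subgroup and close in another, and conclude that CGM works in the first only. The second is the more serious, because it could produce a subgroup claim that a direct estimate of heterogeneity would not support. Only exploratory findings are at stake; the primary DDS comparison does not depend on this plot.

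**Working it through.** **Inputs from section 13, Sample Size**
- SD 1.0: "the standard deviation of the DDS was 1.0 across the three sites in that study". The plan applies this figure to the change score.
- 100 per arm.
- 0.5 as the difference regarded as meaningful.
- 20% dropout, stated for the attendance outcome. It is used below only as a sensitivity case, giving 80 analysed per arm.

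**Assumptions not in the plan**
- Two-sided alpha of 0.05, since none is stated for DDS.
- A normal approximation.
- Two illustrative splits, 50/50 and 15/85. The 15% is the type 1 diabetes share in the 2019 ED billing data (section 13, Feasibility). It is not an enrolment forecast.

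**Step 1. Reproduce the plan's figures.** The plan says "With 100 subjects in each group, we can detect a difference of about 0.40 in the DDS change between the two groups". Detectable difference = (1.960 + 0.842) × 1.0 × √(2/100) = 0.396, which agrees. Power for a difference of 0.5 = Φ(0.5/√(2/100) − 1.960) = Φ(1.576) = 0.94, consistent with the claim of more than 80%.

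**Step 2. Equal split, 50 per arm in each of two subgroups.** The 95% half-widths are:
- Arm mean (the plotted quantity): 1.96 × 1.0/√50 = 0.28
- CGM-minus-control difference in one subgroup: 1.96 × √(2/50) = 0.39
- Difference between the two subgroup effects: 1.96 × √(2/50 + 2/50) = 0.55

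The interval that bears on heterogeneity is twice as wide as the interval on the plot.

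**Step 3. Other cases**

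| Split | Analysed per arm | Arm mean | Subgroup difference | Difference between subgroup effects |
|---|---|---|---|---|
| 50/50 | 100 | ±0.28 | ±0.39 | ±0.55 |
| 50/50 | 80 | ±0.31 | ±0.44 | ±0.62 |
| 15/85 | 100 | ±0.51 / ±0.21 | ±0.72 / ±0.30 | ±0.78 |
| 15/85 | 80 | ±0.57 / ±0.24 | ±0.80 / ±0.34 | ±0.87 |

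For the third row, the last entry is 1.96 × √(2/15 + 2/85) = 0.78. For the fourth it is 1.96 × √(2/12 + 2/68) = 0.87.

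**Step 4. Power for an interaction of 0.5 at 100 per arm**
- 50/50: standard error √(4/50) = 0.283; power Φ(0.5/0.283 − 1.96) = 0.42
- 15/85: standard error √(2/15 + 2/85) = 0.396; power Φ(0.5/0.396 − 1.96) = 0.24

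The interaction detectable with 80% power is 2.802 × 0.283 = 0.79 for the equal split and 2.802 × 0.396 = 1.11 for 15/85.

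**Step 5. Would plotting the difference be enough?** Suppose the true effect is 0.5 in both equal subgroups. Each difference has standard error √(2/50) = 0.2, so each interval excludes zero in the expected direction with probability Φ(0.5/0.2 − 1.96) = Φ(0.54) = 0.705. Exactly one of the two does so with probability 2 × 0.705 × 0.295 = 0.42, although the effects are identical. Plotting differences therefore does not by itself prevent a false subgroup claim. The interaction estimate is needed as well.

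**The case against.** The strongest reply has three parts.

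First, the wording is brief. It does not confine the plots to arm means or rule out a difference column, and the analysis it accompanies is a between-arm comparison. This stands in part. The fair charge is an omission: the difference is not stated, and the authors may have meant to include it.

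Second, arm means with intervals are not uninformative. A reader may infer from this review that the plot could not show a varying effect at all, which would go too far. Subtraction gives each subgroup's point difference, and because the arms are independent an approximate interval can be rebuilt: √(0.277² + 0.277²) = 0.39 in the equal-split case. This also stands. What remains is that the reader must do work the plot should do, and must do it again across subgroups to reach the interaction.

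Third, nothing in the plan says that effects will be judged by whether arm intervals overlap. A reader might infer that the plan adopts such a rule, or that it costs the DDS comparison power. The documents support neither. The whole-sample contrast has its own planned unadjusted comparison and longitudinal model. Overlap is only a foreseeable misuse of the display, and one that errs on the conservative side.

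It can be added that the practical gain is limited, since power for an interaction is low whatever is plotted. That is true, and it is a reason to show the wide interval.

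**Conclusion.** The point holds as a gap in a secondary display. The stated subgroup plot shows arm means with their intervals, while the plan's own DDS contrast is the difference in change between arms. Neither a subgroup-level difference nor an interaction estimate is planned anywhere in the document.

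Under the stated assumptions, the plotted interval is half the width of the one relevant to heterogeneity when the subgroups are equal, and the disparity for the larger subgroup is greater when they are not. These sizes rest on an SD of change of 1.0, two-sided 95% intervals and illustrative splits; actual subgroup sizes are unknown. A larger or smaller SD would scale all the half-widths together and leave the twofold ratio unchanged.

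The primary analyses, the sample size and the DDS power statement are not affected.

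**What to change.** In section 13, Analysis Strategy, revise the forest plot sentence so that:
- for the total sample and each subgroup, the plotted quantity is the CGM-minus-control difference in DDS change with its 95% confidence interval;
- the arm-by-subgroup interaction estimate is reported with its interval, from a model that includes that term;
- arm means are kept as supporting columns;
- the analysis is labelled exploratory, with a note that power for interaction is low (about 42% for an interaction of 0.5 with an equal split and 24% with 15/85, at 100 per arm).

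The DDS subgroups should be named in the same place. Those listed under Provider Data are candidates, but using them for DDS would be a fresh choice for the trial team.

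The cost is a few extra models and a short text edit. No new data, visits or participants are needed.

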9. STUDY TIMELINES*

Patient Subject Participant Involvement Timeline:

- ***Enrollment & Intake Visit: (Day 0)***
 - Informed consent
 - Non-biometric data – Contact information; Intake data points
 - Five-question Problem Areas in Diabetes (PAID-5) scale as well as the 17-question Diabetes Distress Scale (DDS) and supplemental questions will be administered
 - Device training (if randomized to CGM)

- Care coordination to DCOE (all patients)
- ***Outpatient Blood Sugar Monitoring (for intervention group only) (day 0-14)***
 - Continuous Glucose Monitoring – Sensor worn 24 hours a day for up to 14 days.
Data can be uploaded
- ***Follow Up: (~Day 14-21 post ED visit)***
 - Study team will meet patient at follow-up appointment
 - Biometric data – Downloaded
 - Non-biometric data – Five-question Problem Areas in Diabetes (PAID) scale as well as the 17-question Diabetes Distress Scale (DDS) and supplemental survey questions will be administered
 - Compensation (\$10)
- ***6 Months Follow up (no active patient involvement)***
 - Follow-up data points abstracted from electronic health record (EHR)

Provider Subject Participant Involvement Timeline:

- ***Follow Up: (~Day 14-21 post ED visit of patient subjects)***
 - Study team send survey questions to provider subjects immediately after they have a clinic encounter with a patient subject
 - This will be the only time point of participation for provider subjects

Study Timeline: We anticipate that recruitment will be complete by September 30, 2022. Primary data analysis will be complete by the end of March 2023.

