- **Diabetes Center of Excellence Care Coordination:** Study Staff will follow up with ED provider to ensure that patients' have clinically indicated referral to diabetes center of excellence

→ **Appointment scheduling:** RA will make an appointment for the patient before ED discharge, if possible. If this is not possible, RA will contact the patient after discharge to arrange a follow-up appointment.

Outpatient Blood Sugar Monitoring: The CGM will be worn on the participants' upper arm continuously for 14 days (or until it falls off or the patient decides to remove it)

[figure not shown]
Visit #1 (~Day 14-21 Post-Discharge of patient subjects)

- **Documents:**
 - **Visit Data (RA facing)**
 - **Problem Areas in Diabetes (PAID-5) scale/Diabetes Distress Scale and supplemental questions**
 - **Fact sheet for provider subjects**
 - **Provider satisfaction survey**
- **CGM Data:** Biosensor data will be downloaded and reviewed
- **Material Collection:** Study Staff will collect CGM readers
- **Compensation:** Participants will be offered \$10 worth of gift cards to a retail store for completing visit #1.
- **Provider Survey:** immediately following an encounter with a patient subject, the provider taking care of each patient will be contacted by the study team as potential provider subjects. Potential provider subjects subsequently will be sent an email solicitation to participate in a Redcap survey. A fact sheet will be provided with that email. The survey will consist of 4 questions pertaining to their satisfaction with patient subject care coordination and/or their CGM utilization. Providers may be sent multiple surveys if they see multiple subjects who are enrolled in the study. This is the only involvement of the provider subjects.
- **No Shows:** *RAs will reach out to subjects who miss their follow-up appointment to (1) help them reschedule and (2) ask that they fill out the post-intervention questionnaire via an online link (or mailed paper copy or via phone, if desired)*

Follow up Data Collection (~6 months Post-Discharge)

- **Documents:**
 - **6 month follow up datasheet**
- **Data Collection:** The study team will query the EHR to collect follow up data points about enrolled subjects

Figure 1: Procedural Flow Sheet

t

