Contact Info - Contact information will be collected using the Redcap (Contact	- *Identifiable information	- Authorized Study Staff	- N/A	- Contact information will be transferred to the Master Code following

Info) and then transferred to the Master Code				completion of the enrollment and intake visit and the Redcap form will be destroyed
Intake Data Collection Sheet – RA Facing Collected using the Redcap form *Also see Section 12	Study ID# only	Authorized Study Staff	Directly entered by the RA into Recap	1) Destroyed upon completion of data collection verification 2) REDCap database will be archived once results have been published
Intake Data Collection Sheet- Patient Facing Collected using the Redcap form *Also see Section 12	Study ID# only	Authorized Study Staff	Directly entered by the participant into a secure online database using survey mode (REDCap)	1) Destroyed upon completion of data collection verification 2) REDCap database will be archived once results have been published
Info Sheet- Hyperglycemia	- N/A	- N/A	- N/A	- N/A
Info Sheet- Hypoglycemia	- N/A	- N/A	- N/A	- N/A
Info Sheet- CGM	- N/A	- N/A	- N/A	- N/A
Baseline Problem Areas in Diabetes (PAID) scale/ Baseline Diabetes Distress Scale and supplemental questions - Direct entry into REDCap	- Study ID# only	- Authorized Study Staff & Support Personnel	- Directly entered by the participant into a secure online database using survey mode (REDCap)	- REDCap database will be archived once results have been published
2 Week Follow up Data Collection Sheet 1) Collected using the paper form 2) Entered into REDCap *Also see Section 12	1) Study ID# only 2) Same as above	1) Authorized Study Staff 2) Authorized Study Staff & Support Personnel	1) Securely stored in the PI's locked office 2) Secure online database (REDCap)	1) Destroyed upon completion of data collection verification 2) REDCap database will be archived once results have been published
2 Week Problem Areas in Diabetes (PAID) scale/Diabetes Distress Scale and supplemental questions	- Study ID# only	- Authorized Study Staff & Support Personnel	- Directly entered by the participant into a secure online database using survey mode (REDCap)	- REDCap database will be archived once results have been published

- Direct entry into REDCap				
Provider subject email solicitation	-N/A	- Authorized Study Staff & Support Personnel	-N/A	-N/A

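### Section 13 plans growth-mixture clustering of DDS trajectories, but the DDS is scheduled only twice, so each patient supplies one change and no trajectory shape

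*Combined protocol and SAP*

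**What the plan says.** **Analysis.** Under Sample Size, Section 13 says the plan will "fit the trajectory of the DDS change in each group using all DDS measures" in a mixed model for repeated measures (MMRM). Under Analysis Strategy it puts time in months into that model and then adds, on the premise that trajectories exist, that "we are able to use machine-learning approaches, such as growth mixture models, to identify clusters of patients with similar trajectories". The clusters are meant to lie outside the predefined subgroups. No number of classes, selection rule or model constraint is given.

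**Schedule.** Section 9 lists the DDS twice for patients:
- At Day 0: "Five-question Problem Areas in Diabetes (PAID-5) scale as well as the 17-question Diabetes Distress Scale (DDS) and supplemental questions will be administered".
- At the visit headed "Follow Up: (~Day 14-21 post ED visit": "Five-question Problem Areas in Diabetes (PAID) scale as well as the 17-question Diabetes Distress Scale (DDS) and supplemental survey questions will be administered".

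The last step in Section 9 is "6 Months Follow up (no active patient involvement", and Section 11 confirms that it is a query of the health record. For patients who miss the visit, Section 11 has staff "ask that they fill out the post-intervention questionnaire via an online link". That is the same post-intervention form, possibly returned later, and not a third occasion. The table in Section 26 lists a baseline DDS form and a "2 Week Problem Areas in Diabetes (PAID) scale/Diabetes Distress Scale and supplemental questions" form, and no later one. Section 13 itself defines the primary DDS outcome as the change between these two occasions.

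**The concern.** A growth mixture model sorts patients by the shape of their course over time. Two measurements per patient define a starting level and one difference. They cannot separate a patient who improves steadily from one who improves early and then levels off, and they cannot separate true differences in slope from measurement error. If the analysis is run as written, it may report patient types described as trajectories when the data contain none. Section 4 says the trial is to generate preliminary data for later work, so such types could be carried forward.

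**Working it through.** **1. The plan's own DDS figure.** Inputs from Section 13: SD 1.0, 100 per group, detectable difference about 0.40, power above 80% for 0.5. Assumed: two-sided alpha 0.05, since Section 13 states alpha only for attendance.

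- Detectable difference = (1.960 + 0.842) × 1.0 × √(2/100) = 0.396.
- n per group for 0.40 = 2 × (2.802/0.40)² = 98.1, so 99.
- Power at 0.50: 0.50/0.1414 − 1.960 = 1.576, which gives 94.2%.

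The figure reproduces. It rests on one change per patient and uses no trajectory.

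**2. Number of DDS occasions.** Day 0 and about Day 14-21 (Sections 9, 11 and 26): two.

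**3. Identification with a common follow-up time t.** Take the usual linear growth model with intercept variance a, slope variance b, their covariance c, and residual variance s. The two means are fitted by the two fixed effects. What remains is:

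- Var(Y₀) = a + s
- Cov(Y₀, Yₜ) = a + ct
- Var(Yₜ) = a + 2ct + bt² + s

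That is 3 moments for 4 parameters (rank 3). For any d, replacing (a, b, c, s) by (a + d, b + 2d/t², c − d/t, s − d) leaves all three moments unchanged. At t = 0.6 month, starting from illustrative values a = 0.70, b = 0.30, c = 0, s = 0.30:

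| d | a | b (slope variance) | c | s | Var(Y₀), Cov, Var(Yₜ) |
|---|---|---|---|---|---|
| −0.02 | 0.68 | 0.19 | 0.033 | 0.32 | 1.000, 0.700, 1.108 |
| 0 | 0.70 | 0.30 | 0 | 0.30 | 1.000, 0.700, 1.108 |
| 0.20 | 0.90 | 1.41 | −0.333 | 0.10 | 1.000, 0.700, 1.108 |
| 0.29 | 0.99 | 1.91 | −0.483 | 0.01 | 1.000, 0.700, 1.108 |

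Slope variances from 0.19 to 1.91 fit the same data equally well. A third common occasion would give 6 moments and rank 4, which identifies the model.

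**4. Follow-up days that vary.** Assume 160 completers (200 × 0.80, from Section 13's 20% dropout), days spread evenly over 14-21, and a, c and s as in the d = 0 row. The information matrix has entries (n/2) × the average over t of tr(V⁻¹V′ⱼV⁻¹V′ₖ), where V is the 2×2 covariance matrix and V′ⱼ its derivative with respect to parameter j.

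- True slope variance 0.30: standard error 0.89.
- True slope variance 0.10: standard error 0.79.

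The model is formally identified, but the error is about three times the larger value (0.89/0.30 = 3.0) and about eight times the smaller (0.79/0.10 = 7.9).

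**5. What a mixture on two scores can do.** The pair (Y₀, Yₜ) carries the same information as (Y₀, Yₜ − Y₀). A constrained mixture, for example one with no slope variance within class, can be fitted. Its classes are then groups in baseline and change, and change carries measurement error and regression to the mean.

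**The case against.** The case for leaving the text alone has four parts.

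**The plan names an MMRM, not a random-slope model.** This stands. A two-visit MMRM with an unstructured covariance has three covariance parameters for three moments and is identified. A reader might infer that the primary DDS analysis is undermined. The documents do not support that.

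**Non-identification needs a common follow-up time.** This also stands, as a condition. The plan uses continuous time, a Day 14-21 window and possibly later replies from no-shows. Within the window the gain is negligible (step 4). If replies were spread evenly over Day 14-60 (assumed), the standard error for a slope variance of 0.30 would fall to about 0.12. But late replies would come mainly from non-attenders, so time would be mixed up with attendance, itself a primary outcome. Identification would also rest on an assumed straight line.

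**The clustering is permissive and exploratory.** This stands. It is not an objective in Section 4 or an endpoint in Section 10, so it would be wrong to say that the trial fails a stated objective.

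**False classes are not shown to come from two visits.** A reader might infer that the schedule itself produces spurious clusters, because simulations of a single population can yield them almost every time. That inference fails. One simulation assumed a homogeneous, bounded, right-skewed population (mean 2.4, SD 0.97, correlation 0.65, 160 patients, normal mixtures, one versus two classes by BIC, 60 replicates). Two classes were chosen in 100%, 95% and 90% of runs with 2, 3 and 4 visits. A repeat with a skewed homogeneous population gave 98%, 95% and 98%. With less skew (mean 2.8, SD 0.85) the rates were 7%, 0% and 0%. The driver is assumed skewness. Section 13 gives only an SD of 1.0 and a range of 1 to 6, with no mean, skewness or within-patient correlation.

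None of this supplies the missing measurements. The premise that DDS trajectories will be available remains contradicted by Sections 9, 11 and 26.

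**Conclusion.** The point holds in a limited form. Section 13 plans a trajectory-clustering analysis that the DDS schedule cannot support. With a common follow-up time, the usual linear growth model is one variance parameter short (4 against 3). Over Day 14-21 it is identified only very weakly, with a standard error of 0.79 to 0.89 for slope variances of 0.10 to 0.30. Any classes would describe baseline and change and would not be evidence of trajectory types.

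The schedule count comes directly from the documents. The identification result assumes the standard random-intercept, random-slope form, which the plan does not name. The standard errors also assume 160 completers and the illustrative variances in step 3. The consequence is confined to one optional, non-primary analysis and the wording around it. The MMRM, the primary comparison of DDS change and the DDS sample size are not affected.

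**What to change.** In Section 13, delete the growth-mixture clustering from Analysis Strategy, and remove the DDS trajectory wording there and under Sample Size. State that the DDS supports one between-arm contrast: the change from the ED visit to the single follow-up. This keeps the primary outcome as now defined, and the two-visit MMRM can stay. Because Section 13 models HbA1c by reference to the DDS text, check that the HbA1c sentence still reads correctly after the edit.

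The cost is wording only, plus the loss of one optional exploratory analysis. The DDS calculation is unchanged: 99 per group for 0.40, and 94.2% power for 0.50 with 100 per group. If trajectories are really wanted, at least a third DDS assessment would have to be scheduled. That is a design change, and it would not by itself protect a mixture model against skewed scores.
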